Using an alpha of 0.05 and expected cure rates of 50% and 10% in the CHG and placebo arms respectively, 54 subjects (27 per group) would be needed for 85% power to detect a 40% absolute difference in cure ($p<0.05$) between groups. Correcting for a 10% attrition rate, 60 enrolled subjects would be needed. To identify 60 subjects with oropharyngeal colonization, and assuming 33% of patients who are high risk for *S. aureus* colonization will have oropharyngeal colonization, 240 subjects will need to be screened to obtain 80 patients that are oropharyngeally colonized with *S. aureus*. Of these, 75% (n=60) will have *S. aureus* detected by the GeneXpert rapid test and will undergo randomization.

Data Analyses and Data and Safety Monitoring

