The decolonization rate will be calculated as the number of subjects who remain decolonized divided by the number of subjects, and treatment group differences as differences in these rates. The precision of estimated rates and rate differences will be expressed with two-sided confidence intervals calculated as asymptotically normal approximations to binomial or differences in binomial random variables. The level of confidence for these intervals will be 95%. Statistical significance for differences between treatment groups in cure rates will be determined from Fisher’s exact tests. The level of significance for these tests is 0.05. Factors associated with failure of decolonization in the CHG treatment group will also be examined. Based on prior investigations of *S. aureus* colonization from our group and others, these will include demographics (age, gender, race/ethnicity), co-morbidities, measures of hygiene, number of prior skin infections in the prior year, antibiotic use in the prior year, household history of skin infection, adverse effects and tolerability (see Aim 2, below), and treatment adherence. Additionally, we will examine pathogen level predictors of decolonization failure, based on molecular characterization of baseline isolates (see Aim 3). These factors will include baseline colonization with USA300 strain, presence of qac A/B gene, presence of nasal colonization, presence of nasal colonization with a strain identical to the oropharyngeal colonizing strain, and presence of nasal colonization with a strain differing from the oropharyngeal colonizing strain. Associations will be examined using Chi-squared, Fisher Exact test, Wilcoxon rank sum test, or T-test, as appropriate. Small sample size will preclude multivariable analyses of factors independently associated with failure to decolonize. This analysis will be key to identifying factors associated with decolonization failures. Identification of mutable factors associated with decolonization failure will be key towards improving the success of future efforts at oropharyngeal eradication of *S. aureus*. Identification of non-mutable factors will be key towards identifying groups that may need more intense intervention and or education.

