WGS sequencing will addresses several hypothesis in those subjects randomized to CHG oral rinses, specifically: a) strains that are found in the oropharynx at end of treatment (Day 7) will be identical genetically to those at baseline and not represent acquisition of new *S. aureus* strain; b) recolonizing *S. aureus* strains at Day 28 among subjects successfully eradicated at Day 7 will represent (re)colonization with the original isolate that colonized the nasopharynx from the same individual (if present at baseline) or a new *S. aureus* strain not present at baseline and; c) nasal isolates found at baseline and follow up will be identical to synchronously identified oropharyngeal *S. aureus* isolates.

Based on data in older adults,¹⁹ we estimate that of the 30 subjects randomized to the CHG arm, 50% will be decolonized, leaving 15 subjects who will be *S. aureus* positive at the oropharynx at the end of treatment. Based on data of recolonization after decolonization in which recolonization can occur after the decolonization regimen is completed,¹⁰ we estimate that a 10% increase in colonization will be seen at Day 28, i.e., 18 subjects will be oropharyngeally colonized with *S. aureus* at Day 28. Thus, we anticipate we will have results in 33 pairs of oropharynx isolates (15 between baseline and Day 7, and 18 between baseline and Day 28, for a total of 66 isolates total). Additionally we will conduct whole genome sequencing on baseline nasal *S. aureus* isolates associated with the subsequent oropharynx isolates identified at Day 7 and/or Day 28. Based on previous data suggesting that ~45% of those colonized at the oropharynx will be colonized at the anterior nares,^{18,46,95} we estimate an additional 30 (45% x 66) nasal *S. aureus* isolates from baseline and follow-up will be present synchronously with oropharyngeal isolates.

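### Normal-approximation 95% intervals are prescribed for each arm's rate, but with about 2.7 placebo eradications expected in 27 the placebo interval is unreliable, its upper limit tends to be too low, and 0/27 gives 0% to 0%

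*Combined protocol and SAP*

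**What the plan says.** The Aim 1 section on Data Analyses and Data and Safety Monitoring states: "The precision of estimated rates and rate differences will be expressed with two-sided confidence intervals", and describes these as "two-sided confidence intervals calculated as asymptotically normal approximations to binomial or differences in binomial random variables". The confidence level is 95%. The method therefore covers each arm's rate as well as the difference. The section names no score, exact or continuity-corrected interval and has no rule for small or zero counts.

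The comparison between arms is handled separately: "Statistical significance for differences between treatment groups in cure rates will be determined from" Fisher's exact tests at the 0.05 level.

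The Power and Sample Size section supplies the design figures: "expected cure rates of 50% and 10% in the CHG and placebo arms respectively, 54 subjects (27 per group) would be needed". After 10% attrition it asks for 60 subjects. The Aim 3 data-analysis text works with 30 in the CHG arm. Sixty subjects randomized in blocks of four imply 30 in the placebo arm too.

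**The concern.** The Wald interval for a single proportion needs a reasonable number of both events and non-events. The placebo arm is planned with 27 × 0.10 = 2.7 events (30 × 0.10 = 3.0 if all randomized subjects are counted). At such counts the interval is centred too low and its width depends heavily on the observed count, so it tends to stop short of the true rate. If no placebo subject clears colonization, its width is zero.

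Low counts are what the plan expects. Under Baseline visit it argues from an older gargling study that placebo should not decolonize the throat.

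At stake is the stated precision of the placebo eradication rate. The plan presents this trial as the basis for later ones, and the upper limit on eradication without CHG is a figure that a later design would use. That is the limit the method sets too low.

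**Working it through.** **Inputs.** Planned rates of 50% (CHG) and 10% (placebo), 27 completers per arm, 85% power and alpha 0.05 come from Power and Sample Size. The interval method and the 95% level come from Data Analyses and Data and Safety Monitoring. Two-sided testing and the ranges of true placebo rate used below are my assumptions.

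**The plan's own figure.** With pooled rate 0.30 and difference 0.40:

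n = [1.960·√(2·0.30·0.70) + 1.036·√(0.50·0.50 + 0.10·0.90)]² / 0.40² ≈ 22.0

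Continuity correction: (22.0/4)·[1 + √(1 + 4/(22.0·0.40))]² ≈ 26.7, rounded up to 27 per arm. The stated 54 reproduces, and 54/0.90 = 60. Exact Fisher power at 27 per arm is 87.2%. The sample size is not in dispute.

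**Formulas**, with p̂ = x/n and z = 1.96:

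- Wald: p̂ ± z·√(p̂(1−p̂)/n)
- Wilson: [p̂ + z²/2n ± z·√(p̂(1−p̂)/n + z²/4n²)] / (1 + z²/n)
- Clopper-Pearson: from beta quantiles
- Coverage at true rate p: the sum of binomial probabilities over all x whose interval contains p

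**Intervals the placebo arm could produce, n=27:**

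| Eradicated | Wald | Wilson | Clopper-Pearson | Probability at true 10% |
|---|---|---|---|---|
| 0 | 0.0% to 0.0% | 0.0% to 12.5% | 0.0% to 12.8% | 5.8% |
| 1 | −3.4% to 10.8% | 0.7% to 18.3% | 0.1% to 19.0% | 17.4% |
| 2 | −2.5% to 17.3% | 2.1% to 23.4% | 0.9% to 24.3% | 25.2% |
| 3 | −0.7% to 23.0% | 3.9% to 28.1% | 2.4% to 29.2% | 23.3% |

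At a true 10% the Wald lower limit is negative in 66.0% of trials (1 to 3 events). Truncating at 0 removes the impossible value but leaves coverage unchanged, so the substantive faults are the zero-width case and the low upper limit. For 1 to 3 events the Wald upper limit is about 5 to 7.5 points below Wilson's.

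**Coverage of the placebo interval:**

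| n | True rate | Wald | Wilson | Clopper-Pearson |
|---|---|---|---|---|
| 27 | 5% | 74.8% | 95.6% | 99.0% |
| 27 | 10% | 93.8% | 95.3% | 98.5% |
| 27 | 11% | 80.7% | 97.6% | 97.6% |
| 27 | 12% | 84.0% | 96.4% | 98.8% |
| 27 | 15% | 91.5% | 94.8% | 97.4% |
| 27 | 20% | 91.7% | 95.1% | 97.0% |
| 30 | 10% | 80.9% | 97.4% | 99.2% |

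The drop between 10% and 11% has a simple cause. The Wald upper limit for 1/27 is 10.8%, so once the true rate passes that value the outcomes 0 and 1 both miss. At n=30 the limit for 1/30 is 9.8%, so both already miss at 10%, with probability 4.2% + 14.1% ≈ 18.4%.

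**Averages at n=27 over assumed ranges of the true rate:**

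| Range | Mean coverage, Wald | Mean coverage, Wilson | Share of range with Wald below 90% | Wald upper limit too low | Wald lower limit too high |
|---|---|---|---|---|---|
| 5–15% | 87.1% | 95.7% | 66% | 12.2% | 0.6% |
| 10–20% | 89.5% | 95.4% | 48% | 9.5% | 1.0% |

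The nominal miss rate on each side is 2.5%. Wilson coverage is never below 90% in either range.

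**What is not affected.** For the CHG arm at 50% and n=27, Wald and Wilson both cover 94.8%. For the difference at 50% against 10% and 27 per arm, the Wald interval covers 94.2% and Newcombe's 94.9%.

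**The case against.** - **No decision turns on this interval.** The hypothesis is comparative, Fisher's exact test settles it, and readers can recompute an interval from the counts. This stands and is why the point is minor. The plan still commits to reporting the interval.
- **Wald is an inference.** The text names no formula, and a Wilson interval also rests on a normal approximation. Wald is the likelier reading. If another method was meant, the plan has not named it, and the same sentence is needed.
- **At the design point the fault is small.** At 10% and n=27, Wald covers 93.8%, and its low-side misses (5.8%) all come from 0/27. At 10.5%, Wald (94.5%) is marginally better than Wilson (94.3%). This is correct, but neither the true rate nor the final denominator is known in advance, and one percentage point or three subjects takes coverage to about 81%. The ranges 5–15% and 10–20% are assumptions.
- **Wilson's misses are also lopsided, the other way.** Over 5–15% at n=27 its lower limit is too high in 3.8% of trials and its upper limit too low in 0.5%; at exactly 10% the figures are 4.7% and 0%. This is a real trade-off, but the departure from 2.5% is much smaller than Wald's 12.2%.
- **0/27 is uncommon if the true rate is 10% or more.** Its probability is 5.8% at 10%, 1.2% at 15% and 0.2% at 20%. It is 25.0% at 5%.

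**Conclusion.** The concern holds and is minor. As written, the method would give misleading error bars for the placebo rate: coverage that swings between about 81% and 94% close to the planned conditions, an upper limit that is too low several times more often than the nominal 2.5%, and no stated uncertainty at 0/27. This rests on reading the text as the Wald interval and on a true placebo rate somewhere near the planned 10%, not exactly on it. Only reported precision is affected. The primary test, type I error, power, sample size, CHG interval and interval for the difference need no change on this account.

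**What to change.** In Data Analyses and Data and Safety Monitoring, name the single-arm method, for example: *Two-sided 95% confidence intervals for each arm's decolonization rate will be Wilson score intervals.* Clopper-Pearson is acceptable if guaranteed minimum coverage is preferred. The interval for the difference and Fisher's exact test can stay as written.

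The cost is one sentence; both methods are in standard software and need no new data. Each has a price. At 10% and n=27 the mean width is 24.9 points for Clopper-Pearson, 22.7 for Wilson and 19.6 for Wald truncated at 0. Wilson under-covers at very low true rates (89.9% at 2%, about 84% near 0.7%), so Clopper-Pearson is the safer choice if the team expects almost no placebo eradication.

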Subjects will also be swabbed for *S. aureus* and MRSA colonization at the anterior nares and oropharynx. Testing will be performed using two methods: direct microbiology cultures and rapid molecular testing. Microbiologic cultures will be performed by culturing swabs from sites taken to identify *S. aureus* and MRSA carriage will be transported to the research microbiology laboratory at LA BioMed at Harbor-UCLA and plated within 24 hours of collection. Swabs will be processed for *S. aureus* using blood agar and CHROMagar plates for rapid identification of *S. aureus* and MRSA. All *S. aureus* and MRSA isolates will be banked for pulse-field typing, determination of SCCmec type, and presence of the PVL locus (*lukF-PV* and *lukS-PV*). Rapid molecular testing will be performed using the GeneXpert MRSA/SA platform, which is currently available at our site.

Upon confirmation of eligibility, the study coordinators will call the pharmacy to randomize the participant and obtain the oral rinse. The randomization assignment list will be generated in advance by pharmacy. Randomization procedures by an assignment list will be prepared by a computer method. To ensure adequate balance of subjects between the CHG and placebo groups, treatment allocation will be assigned using a random number generation with randomization of blocks of four subjects each. The randomization list will be kept by the pharmacy and treatment allocation randomization will not be shared with either the study staff or patients. The research pharmacists will dispense the appropriate oral rinse to the participant and their parent/guardian. Placebo will be created using the inert vehicles components of CHG, as has been done previously.⁸⁹ Participants and their parent/guardian will be given detailed instructions on the use of the oral rinse both verbally and in a handout in either English or Spanish as preferred by the participant and their parent/guardian.

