Participants will be asked to come to the research clinic 7 days after initiation of oral CHG, i.e., at the end of their treatment (Visit 2). A subsequent visit will occur at 28 days (Visit 3). The purpose of these visits is to ascertain oropharyngeal eradication of *S. aureus* both short term (primary study outcome) and longer term. Based on previous investigations conducted at our center(s), we estimate a 10% attrition rate.^{75,77,78,81,82} At Visit 2, participants will be swabbed the nares and oropharynx for the presence of *S. aureus* and to complete a follow-up survey about any recurrent infections, new medical history, or receipt of antibiotics. At Visit 3, participants will return to the research clinic to complete a follow-up survey. Study staff will also call all subjects remind them of their upcoming study appointments and at days 14 and 21 to address any questions the participant or their parent/guardian may have about the study. Adverse events will be measured at each scheduled and unscheduled (see below) follow-up visits. Adverse events will be measured using the Medical Dictionary for Regulatory Activities Terminology (MedDRA) version 14.0 or later terms.

Unscheduled visits

If participants or their parent/guardian experience potential adverse drug events that occur during the follow up period, subjects or their parent/guardian will be encouraged to contact study staff. If the event may be of clinical concern, the event will be referred to a study physician and the oral rinse discontinued, if applicable. If deemed necessary by the study physician or the subjects' primary physician, participants will be asked to return to the research clinic for evaluation by a study investigator.

Aim 1: Determine the efficacy of oropharyngeal decolonization among children suffering from CA-MRSA and other *S. aureus* skin infections

To determine if oropharyngeal *S. aureus* colonization can be eradicated, we will perform a prospective, double blind randomized controlled clinical trial of 0.12% oral chlorhexidine (CHG) oral rinse versus placebo for children age 5-17 with *S. aureus* oropharyngeal colonization. We hypothesize that 0.12% CHG rinse will

reduce oral *S. aureus* colonization better than placebo treatment. The findings from this Aim will provide “proof of principle” data on the ability of oral antiseptics to eradicate oropharyngeal *S. aureus* colonization in children.

Power and Sample Size

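### Fisher's test for Day 7 eradication is valid and adequately powered; a score interval and, separately, Boschloo's exact test would be cheap improvements

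*Combined protocol and SAP*

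**What the plan says.** In Aim 1, Data Analyses and Data and Safety Monitoring: "Statistical significance for differences between treatment groups in cure rates will be determined from" Fisher's exact tests, and "The level of significance for these tests is 0.05". The same paragraph describes the precision of the rates and of their difference by "two-sided confidence intervals calculated as asymptotically normal approximations to binomial or differences in binomial random variables", at the 95% level. It does not say whether the test is two-sided.

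In Aim 1, Power and Sample Size, the plan takes "expected cure rates of 50% and 10% in the CHG and placebo arms respectively" and states that "54 subjects (27 per group) would be needed for 85% power to detect a 40% absolute difference in cure". It then adds: "Correcting for a 10% attrition rate, 60 enrolled subjects would be needed". The Follow-up visits section repeats the loss figure ("we estimate a 10% attrition rate"). The Baseline visit section says that "treatment allocation will be assigned using a random number generation with randomization of blocks of four subjects each".

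Neither an unconditional exact test nor a score-type interval is mentioned.

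**The concern.** Fisher's test conditions on both margins of the 2x2 table. With about 27 children per arm, few tables are possible for each margin, so the true type I error lies well below the nominal 5%. The normal-approximation interval errs the other way: in samples this small it tends to be slightly too short. The plan pairs the two.

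Two modest things are at stake. Part of the permitted 5% error goes unused, and with it a little power. The report can also show a non-significant p-value beside an interval that excludes zero. That would be awkward to present, although the plan's decision rule would still settle the result.

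**Working it through.** **Inputs.** From the plan: alpha 0.05, 50% v 10%, 27 completers per arm, 60 randomized, 10% attrition, blocks of four. Assumed here:
- a two-sided test, to match the two-sided intervals;
- 1:1 allocation, so 60/4 = 15 blocks and 30 per arm;
- completers per arm independently Binomial(30, 0.9);
- analysis of completers.

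**Reproducing the plan's figure.** With p̄ = 0.30 and Δ = 0.40:

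n = [1.960·√(2·0.30·0.70) + 1.036·√(0.50·0.50 + 0.10·0.90)]² / 0.40² = (1.270 + 0.604)² / 0.16 ≈ 22.

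The continuity correction gives (21.96/4)·[1 + √(1 + 4/(21.96·0.40))]² = 26.7, so 27 per arm. This matches the plan. One-sided versions give 18, or 23 with the correction. For attrition, 54/0.90 = 60, which also matches.

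**Method.** All 2x2 tables were enumerated for each pair of arm sizes. Maximum size is the largest rejection probability over a common eradication rate π. The Boschloo p-value is max over π of P_π(p_F(X) ≤ p_F(observed)), where p_F is the two-sided Fisher p-value.

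**Test: power at 50% v 10%**

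| Completers (CHG/placebo) | Fisher | Boschloo |
|---|---|---|
| 27/27 | 87.2% | 92.0% |
| 26/28 | 89.8% | 91.0% |
| 28/27 | 89.9% | 91.3% |
| 25/29 | 91.5% | 91.6% |
| 30/30 | 91.35% | 93.04% |
| Average over attrition | 89.5% | 91.6% |

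The average gain is 91.6 − 89.5 = 2.1 points. The median over splits is 1.5 points (10th to 90th percentile 0.3 to 4.5). The unrounded 27/27 gain is 91.97 − 87.25 = 4.7 points, but exactly 27/27 occurs in only about 6% of trials. At 40% v 10%, a scenario assumed here, the averages are 68.31% and 72.95%, a gain of 4.6 points.

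**Test: maximum size.** Fisher averages 3.5% (2.6% at 27/27, 3.6% at 26/28). Boschloo averages 4.8% and never exceeds 5%. In all 119 splits examined, covering 99.99% of the attrition distribution, Boschloo rejects every table that Fisher rejects.

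**Interval: coverage of the difference at 50% v 10%.** The normal approximation covers 94.2% at 27/27, 93.6% at 26/28 and 93.7% averaged over attrition. Over 27/27, 26/28, 28/26, 27/26 and 28/27 it covers 93.3 to 94.2%; the score interval covers 94.7 to 95.5%.

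**Mismatch: interval excludes zero, test not significant**

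| Pairing | Average, 50% v 10% | 27/27, 50% v 10% | Average, 40% v 10% |
|---|---|---|---|
| Fisher + normal (as planned) | 4.2% | 6.3% | 9.6% |
| Boschloo + normal | 2.1% | 1.6% | 5.0% |
| Boschloo + score | 0.8% | 0.5% | 2.0% |

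If Fisher is kept and only the interval changes, the average mismatch at 50% v 10% follows from these figures. It is the Boschloo + score mismatch (0.83%), plus the tables that Boschloo rejects and Fisher does not (2.10%), less at most 0.09% where Boschloo rejects but the score interval includes zero. That gives 2.8 to 2.9%. At 27/27 the same sum is about 0.52 + 4.72 = 5.2%.

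**Example.** Take 10/27 v 3/27. The difference is 7/27 = 0.259, with standard error √(0.370·0.630/27 + 0.111·0.889/27) = 0.111. The planned interval is 0.259 ± 1.96·0.111 = 0.042 to 0.477, yet Fisher's p is 0.0537. Boschloo's p is 0.0306 and the score interval is 0.031 to 0.472. This table has probability 0.015 at the planned rates.

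**The case against.** The strongest reply is that the plan keeps every commitment it makes. The test is exact, it controls type I error, and its power exceeds 85% both at 27/27 and on average. On that view the rest is preference for a less familiar method. All of the facts in this reply stand, so the point can only be an optional improvement.

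A reader might infer that the primary result could be read in two ways. The documents do not support that. They give the intervals the task of expressing precision and give significance to Fisher's test alone, so there is one decision rule.

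A reader might also take the planned interval to be badly wrong, because its maximum size, read as a test, is 7.6% at 27/27 and 6.5% on average. That is a worst case over all common rates, and the 27/27 figure arises when both arms are at 50%. With both arms at the plan's placebo rate of 10%, the size is 5.2% at 27/27 and 5.4% at 26/28. At the planned rates the coverage shortfall is about one point.

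Two further objections stand in part. The power gain depends on the split and almost vanishes at 25/29. The remedy is also imperfect: the score interval is approximate, with maximum size averaging 5.3%, and it leaves some mismatches.

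**Conclusion.** The planned test is valid and meets its stated power, and the decision rule contains no error. A claim that the trial is underpowered, or that its conclusion would be ambiguous, goes beyond the documents.

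Two independent, low-cost improvements hold:

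- **Interval.** A score interval recovers about one point of coverage at the planned rates. On its own it lowers the average mismatch with Fisher from 4.2% to just under 3%. Most of what remains comes from Fisher's conservatism.
- **Test.** Boschloo's test gains about 2 points of power on average at 50% v 10%, and about 4.6 at the assumed 40% v 10%, with type I error still at or below 5%. The 4.7-point gain at exactly 27/27 should not be quoted as typical.

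The averages rest on a two-sided test, independent 10% loss in each arm from 30/30, and analysis of completers. The test conclusion survives a change in the last of these. If all 60 are analysed with missing counted as failure, the rates become 0.9·50% = 45% and 0.9·10% = 9%. Power is then 86.1% for Fisher and 88.4% for Boschloo, a gain of 2.3 points.

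**What to change.** **Interval, whether or not the test changes.** For the rate difference, replace the normal-approximation interval with a 95% Miettinen-Nurminen score interval. Keep the statement that significance comes from the exact test, because the interval will not always agree with it.

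**Test, as a separate choice made before unblinding.** Suggested wording: *The primary comparison of Day 7 eradication uses Boschloo's unconditional exact test, two-sided, alpha 0.05, with tables ordered by the two-sided Fisher p-value. Statistical significance is taken from this test alone; Fisher's p-value is reported as a sensitivity analysis.* If Fisher's test is kept instead, state that it is two-sided.

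**Cost.** Two or three sentences, with no extra children, visits or data. The downsides are lesser familiarity and a software check. Some routines double the one-sided p-value by default, and other or custom code may be needed for the stated ordering. At 26/28 the doubled form misses two tables that Fisher rejects: for 4/26 v 0/28 its p is 0.056 against Fisher's 0.047. The stated ordering is chosen so that no Fisher rejection is lost. It is not always the more powerful form: at 26/28 the doubled form has 92.2% power against 91.0%.

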We have several secondary hypotheses: a) decolonization of oropharyngeal *S. aureus* colonization with 0.12% CHG will be sustained at 28 days; b) recolonization of the oropharynx will come from isolates that colonize patients nose and not from development of antimicrobial resistance, including the emergence of CHG-resistant *S. aureus* strains that contain the *qac A/B* genes; and c) predictors of failure to decolonize with CHG will include poor treatment adherence, nasal *S. aureus* colonization, and younger age.

If our primary hypothesis is correct, findings will form the foundation for a larger, randomized, prospective, multi-center, placebo-controlled clinical trial comparing skin, nasal, and oropharyngeal decolonization vs. standard of care decolonization regimen for the prevention of recurrent *S. aureus* skin infections. If oral CHG rinse is unable to decolonize the oropharynx, then other more aggressive oropharyngeal *S. aureus* colonization eradication strategies in children will need to be tested.

B. Specific Aim(s) of the Project

1) Determine the efficacy of oropharyngeal decolonization among children with a history of CA-MRSA, CA-*S. aureus* or skin and soft tissue infection (SSTI). To determine if oropharyngeal *S. aureus* colonization can be eradicated, we will perform a randomized, double blind placebo-controlled controlled clinical trial comparing 0.12% oral chlorhexidine (CHG) oral rinse to placebo among children age 5-17 with *S. aureus* oropharyngeal colonization. We hypothesize that 0.12% CHG rinse will reduce oral *S. aureus* colonization better than placebo treatment. Our findings will provide “proof of principle” data on the ability of oral antiseptics to eradicate oropharyngeal *S. aureus* colonization in children.

2) Assess the safety, tolerability, and compliance of oropharyngeal decolonization among children and their caregivers. Using a structured instrument, we will survey trial participants and their parents/guardians on side effects, tolerability, and adherence of the 0.12% oral CHG rinse and placebo. Findings will serve as a counterpoint to any benefits derived from oral decolonization.

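### The primary test is valid and meets its planned power, but leaves baseline nasal S. aureus status unused; an exact test stratified on it is a cheap, modest and optional gain

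*Combined protocol and SAP*

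**What the plan says.** - **Primary comparison** (Aim 1, Data Analyses and Data and Safety Monitoring): "Statistical significance for differences between treatment groups in cure rates will be determined from" Fisher's exact tests at the 0.05 level. The rate difference is "expressed with two-sided confidence intervals calculated as asymptotically normal approximations" to the binomial. Neither uses a baseline factor.
- **Sample size** (Power and Sample Size): "54 subjects (27 per group) would be needed for 85% power to detect a 40% absolute difference in cure", with "expected cure rates of 50% and 10% in the CHG and placebo arms respectively". Then: "Correcting for a 10% attrition rate, 60 enrolled subjects would be needed".
- **Randomization** (Baseline visit): blocks of four, with no stratification factor named.
- **Nasal status as a predictor** (Hypotheses to be Tested): "predictors of failure to decolonize with CHG will include poor treatment adherence, nasal" S. aureus colonization and younger age. The Aim 1 analysis section lists nasal colonization again, among factors to be examined for failure in the CHG group.
- **Measurement** (Baseline visit): nares and oropharynx are both swabbed after consent, for rapid testing and for culture, before the pharmacy is called to randomize.
- **Frequency** (Aim 3, Data Analyses): about "45% of those colonized at the oropharynx" are expected to carry S. aureus in the nares as well. The Scientific Abstract implies 50%.

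The remark that small numbers rule out multivariable work concerns the search for predictors of failure. It does not concern the treatment comparison.

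**The concern.** The plan expects nasal carriers to fail more often with CHG, expects nearly half the children to be carriers, and will know each child's status before allocation. The treatment comparison uses none of this. In a trial of 54 completers, a prognostic baseline factor can add power at no cost in patients. It also gives a pre-specified answer if the arms differ by chance on that factor.

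The usual reason not to adjust in so small a trial is sparse data: 10% of 27 is 2.7 expected placebo cures, too few for a regression model. That reason does not reach an exact conditional test with one two-level stratum, which fits no model and needs no large-sample approximation.

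**Working it through.** **1. The plan's own figure.** Inputs: alpha 0.05, power 85%, 50% vs 10%. Two-sided testing is assumed, since the plan states it only for the intervals.

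Uncorrected n per arm = [1.96·√(2·0.3·0.7) + 1.036·√(0.5·0.5 + 0.1·0.9)]² / 0.4² = (1.270 + 0.604)² / 0.16 ≈ 21.96, so 22.

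With continuity correction: (21.96/4)·[1 + √(1 + 4/(21.96·0.4))]² = 5.49·(2.206)² ≈ 26.7, so **27 per arm**. Then 54/0.9 = **60**. Both figures reproduce.

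**2. Power of the planned test.** Full enumeration of two-sided Fisher at 27 per arm gives 87.2% at 50% vs 10%. The stated 85% is met.

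**3. The stratified test.** Condition on the number of cures within each nasal stratum. Convolve the two hypergeometric distributions of CHG-arm cures, and sum the probabilities no larger than that of the observed total. Simulation: 27 per arm, 45% carriers, unstratified allocation, overall rates held at 50% and 10%, 40,000 trials per scenario (error about 0.2 points). The odds ratio (OR) for failure in nasal carriers is an **assumption**, because the documents give none.

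| Assumed nasal effect | Fisher | Exact stratified | Gain (points) |
|---|---|---|---|
| OR 1 | 87.4% | 88.9% | 1.5 |
| OR 2, both arms | 87.3% | 89.7% | 2.5 |
| OR 3, both arms | 87.2% | 90.5% | 3.2 |
| OR 5, both arms | 87.3% | 91.8% | 4.5 |
| OR 2, CHG arm only | 87.2% | 89.1% | 1.9 |
| OR 3, CHG arm only | 87.1% | 89.6% | 2.5 |
| OR 5, CHG arm only | 87.3% | 90.4% | 3.1 |

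(Gains are taken from unrounded values.) Type I error of the stratified test is 1.9-2.2% at a 10% null rate and 3.3-3.4% at 30%.

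**4. Where the gain comes from.** At OR 1 nasal status carries no information, so the 1.5 points there can come only from a less discrete reference distribution. Using mid-p versions of both tests largely removes discreteness. The gain is then -0.6 points at OR 1, +0.1 at OR 2, +0.9 at OR 3 and +2.1 at OR 5.

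**5. Precision of the estimate.** Variance of the Mantel-Haenszel risk difference divided by that of the crude difference: 1.02 (OR 1), 1.00 (OR 2), 0.97 (OR 3), 0.93 (OR 5).

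**6. Chance imbalance.** The SD of the between-arm difference in nasal carriage is √(2·0.45·0.55/27) = 0.135, or 13.5 points. Take OR 3, with cure rates of 62.0% in non-carriers vs 35.3% in carriers on CHG, and 14.0% vs 5.1% on placebo. These average to the planned rates: 0.55·62.0 + 0.45·35.3 = 50.0, and 0.55·14.0 + 0.45·5.1 = 10.0. Each arm's carriage has SD √(0.45·0.55/27) = 0.096. Carriage variation therefore adds √[(0.096·0.267)² + (0.096·0.089)²] ≈ 0.027 to a crude difference whose SD is 0.112, about (0.027/0.112)² ≈ 6% of the variance.

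**7. A smaller true effect.** At 40% vs 10%: 63.4% vs 67.4% (OR 1), 63.0% vs 69.6% (OR 3), 63.3% vs 72.2% (OR 5).

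**8. In children.** The stratified test matches Fisher's 87% at about 26 per arm (OR 1), 25 (OR 3) or 24 (OR 5) instead of 27.

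**The case against.** A reader might infer that the primary analysis is wrong or underpowered. The documents do not support that. Randomization makes the unadjusted Fisher test valid, chance imbalance in nasal carriage is already part of its error rate and of the interval, and the stated power is exceeded.

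A reader might also infer that the plan forfeits material precision, or that nasal status is a strong predictor. Neither is supported. The variance hardly moves. No document gives an effect size, and the hypothesis is about failure with CHG, so an effect in the placebo arm is a further assumption. Large gains need extreme inputs: CHG cure of 75% in non-carriers against 19% in carriers is an odds ratio of (0.75/0.25)/(0.19/0.81) ≈ 13.

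The strongest counter-argument is that if Fisher's conservatism is the problem, no covariate is needed. Enumeration of an unstratified Boschloo test at 27 per arm, with maximum size held below 5%, gives 92.0% power at 50% vs 10% and 73.5% at 40% vs 10%. That equals or beats the stratified test for odds ratios up to 5. This stands. The remaining reasons to stratify are that it uses information the plan itself considers relevant and settles in advance how nasal imbalance is handled.

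It also stands that nasal status is measured by two assays that can disagree, so yes/no is not yet a definition. In addition, the treatment difference would vary by stratum: 62.0 - 14.0 = 48 points vs 35.3 - 5.1 = 30 points in the OR 3 example. A single Mantel-Haenszel difference is then a weighted average and should be described as one.

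**Conclusion.** The point holds as an optional improvement. The stratified exact test had more power than Fisher in every scenario run, with type I error below 5%. At the planning rates the gain is about 1.5 points with no nasal effect, 2 to 5 points for odds ratios of 2 to 5, and 2 to 3 points if the effect is confined to the CHG arm. Much of it reflects reduced discreteness rather than prognostic information. The gain is about 4 to 9 points at 40% vs 10%, so it matters most if the assumed effect proves optimistic.

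These sizes rest on 45% nasal carriage, 27 completers per arm, two-sided testing and assumed odds ratios. Confidence is moderate: the plan's text is clear, but the strength of nasal status as a predictor is unknown.

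**What to change.** In the Aim 1 data analysis section, before unblinding:

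- Make the primary test an exact conditional test of treatment stratified by baseline nasal S. aureus (yes/no).
- Define the stratum by one named assay, for example the pre-randomization rapid test on the nares swab, and say how an invalid or missing result is handled.
- Report the Mantel-Haenszel risk difference with its 95% CI as the matching estimate, stating that it averages over the two strata.
- Keep the unstratified Fisher test as a sensitivity analysis.

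The cost is a few sentences of analysis text, with no new data, visits or children. The downsides are a slightly less simple primary test and, if nasal status is not prognostic, about 2% more variance in the estimated difference. If the sponsor prefers the Fisher test, it can stand without harm to validity or to the stated power.
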